There will be two aims to the study. The first aim will include using the existing TELE-STAT and TELE-ASD-PEDS tools to assess and evaluate their acceptability/feasibility, clinical value for remote observation, and challenges that warrant revision. We will then use this data to modify the TELE-STAT and TELE-ASD-PEDS instruments to optimize fluid use. In the second aim, we will deploy the refined TELE-STAT (n=60) and TELE-ASD-PEDS (n=60) with new samples of clinically referred children (15-36 months of age) and rigorously evaluate their ability to facilitate accurate telemedicine supported diagnostic decision making. Remote clinicians will utilize telemedicine tools and generate ratings of diagnostic certainty, which will be compared to blinded comprehensive assessments using gold-standard tools. We will critically evaluate each tool independently and compare the characteristics of these tools to each other in addition to gathering feedback from participating families on acceptability and use.

Expected duration of the study

2 years

Accrual Goal: What is your total accrual goal at Vanderbilt?

60 parents and 60 children in Aim 1; 120 parents and 120 children in Aim 2

Total number of participants stated in the protocol to be studied at all sites (regardless of PI).

180

Aim 1:

Inclusion Criteria:

- Previously evaluated and diagnosed with autism or other developmental delay
- \geq 15 months of age and \leq 36 months of age
- Parental (or other legal guardian) informed consent to participate
- English speaking

Exclusion criteria:

- significant sensory impairment (e.g., hearing or visual impairment, child not yet walking) or medical complexity that would make assessment instruments invalid.

Aim 2:

Inclusion Criteria:

- \geq 15 months of age and \leq 36 months of age
- Concerns for autism or other developmental delay
- Parental (or other legal guardian) informed consent to participate
- English speaking

Exclusion criteria:

- Significant sensory impairment (e.g., hearing or visual impairment, child not yet walking) or medical complexity that would make diagnostic instruments invalid. These children will be referred to appropriate VUMC medical providers for diagnostic consultation and follow-up.

Behavioral Observations

Aim 1:

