Each child and their caregiver(s) will participate in one appointment. After consent, they will be randomly assigned to one of two telemedicine procedures (TELE-STAT or TELE-ASD-PEDS). The child and parent will be led through the screening tool by a remote psychologist (approximately 30 to 45 minutes). The telemedicine procedure, regardless of which one the family is assigned to) involves behavioral interactions that are coded by the examiner on paper forms. Parents will be in the same room as their child at all times and will also be asked to interact with their child in specific ways in order to elicit social, communication, and play skills in their child.

Aim 2:

Each child and their caregiver(s) will participate in one appointment. The appointment will include 2 parts: 1. telemedicine tool and 2. gold standard diagnostic evaluation. After consent and being randomly assigned to one of two telemedicine procedures, the child and parent will be led through the screening tool by a remote psychologist (approximately 45 minutes to 1 hour). Following the telemedicine procedure, the child will receive a gold standard diagnostic evaluation (2 to 3 hours) in person by a licensed clinician.

Behavioral Observation will be conducted in both the telemedicine and gold standard evaluations. This will be done as part of the TELE-STAT (telemedicine autism screener), TELE-ASD-PEDS (telemedicine autism screener), and ADOS-2 (gold standard autism test). Both the telemedicine screeners and the ADOS-2 procedures involve behavioral interactions that are coded by the examiner on paper forms. Parents will be in the same room as their children at all times and will also be asked to interact with their child in specific ways in order to elicit social, communication, and play skills in their child.

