The TELE-STAT takes approximately 30 minutes. Parents will be walked through each task by a remote clinician. Children interact with their parent to complete 12 items (2 play tasks, 2 requesting tasks, 4 object spectacle/joint attention tasks, 4 imitation tasks). Behaviors are coded on a form based on the examiner's observations. The STAT yields a total score of 0-4 that indicates level of ASD risk. TELE-ASD-PEDS takes approximately 30 minutes. Parents will be walked through each task by a remote clinician. Children interact with their parent to complete 11 items (play tasks, directing attention tasks, requesting tasks). Behaviors are coded on a form based on the examiner's observations. The instrument is scored based on a 7-item rating scale. Mullen Scales of Early Learning (MSEL): The MSEL takes approximately 30 minutes to complete for children with suspected ASD who are within this age group. The MSEL is a standardized, well- validated measure of cognitive and developmental skills. Children are presented with standardized prompts within four domains: Visual Reception (nonverbal problem solving, e.g., putting pieces in a puzzle), Fine Motor (manipulating objects with hands; e.g., stacking blocks), Receptive Language (understanding words; e.g., following instructions), and Expressive Language (using words; e.g., naming objects). Responses are coded as correct or incorrect based on the MSEL manual. Scores are standardized. ADOS-2: The ADOS-2 takes approximately 30-45 minutes to complete. There are 5 versions of the ADOS-2 dependent on a person's age and language level. All children who participate in this study will complete the Toddler Module, Module One, or Module 2. These modules, designed for very young children with limited verbal skills, involve activities such as blowing bubbles, requesting a snack, playing with developmentally appropriate toys (cars, blocks), and engaging in games. Behaviors are coded based on the trained examiner's observations and rated on a scale of 0-2 or 0-3, dependent on the item. The ADOS-2 yields a total score of 0-30 that indicates level of ASD risk. The ADOS-2 will be completed by a trained examiner. Parents can be asked to participate in a couple of the tasks.

Randomization

All participants will be randomized to TELE-STAT and TELE-ASD-PEDS using a random number generator program based upon enrollment order.

Blinding**Aim 1:**

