necessary for honing the procedures utilized in our rigorous evaluation of measure use in Aim 2. Although we are examining diagnostic agreements in this study, the larger rigorous, blinded evaluation described in Aim 2 is ultimately necessary to adequately test and understand the potential added value of these tools.

Specific Aim 2: After optimizing use and administration characteristics, we will deploy the refined TELE-STAT (n=60) and TELE-ASD-PEDS (n=60) assessment tools with clinically referred, undiagnosed children and rigorously evaluate their ability to facilitate accurate telemedicine supported diagnostic decision making. Secondary analyses will also compare the characteristics of these tools across these independent samples as well as potential scoring thresholds for the instruments for subsequent evaluation. Our team of 10 clinical providers will be asked to complete 6 remote evaluations utilizing TELE-STAT and 6 remote evaluations with TELE-ASD-PEDS. At the end of the procedure, the psychologist will complete ratings of clinical best estimate (CBE) diagnosis and diagnostic certainty (Yes / No ASD; Yes / No / Uncertain classification, as well as Likert rating of certainty ranging from 1= 'uncertain' to 5 = 'very certain'). Families will then immediately participate in a blinded in-person comprehensive assessment conducted by a different licensed psychologist. This assessment will include administration of a measures of cognitive functioning (MSEL), adaptive behavior (VABS-3), autism symptoms (ADOS-2), as well as clinical interviewing surrounding medical, behavioral, and developmental history. The blinded provider will then independently assign diagnostic and certainty ratings, and provide clinical information to the family.

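### Aim 2 randomises tools by enrollment order with no stated link to the clinician or guarantee of equal totals, so the planned 6 + 6 sessions per clinician and 60/60 overall are not secured

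*Combined protocol and SAP*

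**What the plan says.** The Randomization section reads: "All participants will be randomized to TELE-STAT and TELE-ASD-PEDS using a random number generator program based upon enrollment order". It covers both aims and names no block size, stratum, fixed total, ratio or clinician factor.

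Under Statistical Design and Power, Specific Aim 2, the operator structure is: "Our team of 10 clinical providers will be asked to complete 6 remote evaluations utilizing TELE-STAT and 6 remote evaluations with TELE-ASD-PEDS". The same paragraph sets the group sizes: "we will deploy the refined TELE-STAT (n=60) and TELE-ASD-PEDS (n=60) assessment tools". The accrual goal agrees, at 120 children in Aim 2.

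Behavioral Observations, Aim 2, puts allocation inside a single appointment: "After consent and being randomly assigned to one of two telemedicine procedures, the child and parent will be led through the screening tool". It does not say when or how the remote psychologist for that appointment is chosen.

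The tool-against-tool comparison is listed among the secondary analyses of Specific Aim 2. It is to be done by chi-square, with no clinician term mentioned. The plan adds that it lacks the power to study variation linked to clinician characteristics.

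**The concern.** The plan sets a target in which every clinician uses both tools equally often, but the only stated allocation rule does not refer to the clinician. The site could follow the list and miss 6 + 6, or it could steer towards 6 + 6 by an unwritten method.

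This matters because the Aim 2 outcome is the clinician's own diagnosis and certainty rating. Clinicians plausibly differ in threshold and confidence. If one of them does mostly TELE-STAT sessions and another mostly TELE-ASD-PEDS, part of the difference between clinicians appears as a difference between tools. The planned chi-square would not remove it. Steering by discretion is worse: if someone who knows the tool and the family picks the rater, the pairing of rater and child may depend on the child.

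**Working it through.** **Inputs from the documents.** 10 clinicians; 6 sessions per tool each; 60 children per tool; 120 children in Aim 2; roughly 2/3 of referrals with ASD.

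**Assumptions.** 1:1 allocation, exactly 12 children per clinician, no dropout or replacement. Steps 2 and 3 also assume that clinicians are booked independently of the tool.

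**1. The plan's own figure.** 10 × 6 = 60 per tool, and 10 × 12 = 120 in total. Both reproduce.

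**2. Simple 1:1 randomisation.**
- Exact 60/60 overall: C(120,60)/2^120 = 0.073.
- One clinician at 6/6: C(12,6)/2^12 = 924/4096 = 0.226, so about 2.3 of 10 clinicians are expected to reach it.
- All ten at 6/6: 0.2256^10 = 3.4 × 10^-7.
- One clinician at 9/3 or worse: 0.146. At least one of ten: 1 − (1 − 0.146)^10 = 0.79.

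**3. A list fixed at 60/60.**
- One clinician at 6/6: C(60,6)²/C(120,12) = 0.238, so about 2.4 of 10 are expected.
- All ten at 6/6: C(12,6)^10/C(120,60) = 4.7 × 10^-6.
- By simulation of 40,000 lists: at least one clinician at 9/3 or worse in 72%; mean total departure from quota (sum of |n − 6|) 12.8.

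**4. Can 6 + 6 be reached without changing any tool assignment?** Yes, under rules that the plan does not state.
- Clinician chosen after the tool is drawn, from those with quota left for that tool: 6/6 for all ten in 100% of simulated lists if the list is fixed at 60/60 or blocked. With simple randomisation this works only when the totals happen to be 60/60, about 7%.
- Blocks of 4 or 12, with each clinician taking 12 consecutive enrollees: 6/6 for all ten in 100%.
- Blocks of 4 or 12 with clinicians in rotation or in random order: only about 2.3 to 2.4 of ten clinicians reach 6/6.

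**5. Noise from chance imbalance if the list is followed.** Take a fixed 60/60 list and clinician rates that vary with standard deviation σ. The documents give no σ, so a range is used.
- Variance of one clinician's count on one tool: 12 × 0.5 × 0.5 × 108/119 = 2.72.
- Contribution to the between-tool difference: the variance is σ² × 10 × 2.72 × (2/60)² = 0.0302σ², so the SD is 0.174σ.
- For σ of 5, 10 and 20 points: 0.9, 1.7 and 3.5 points.
- Standard error of the difference at an assumed 60% outcome rate: √(2 × 0.6 × 0.4/60) = 8.9 points.
- Share of variance: (0.9/8.9)² ≈ 1%, (1.7/8.9)² ≈ 4%, (3.5/8.9)² ≈ 15%.

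**The case against.** The strongest reply is that the documents are silent here rather than in contradiction. Three parts of it stand.

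- A reader might infer that 6 + 6 cannot occur unless staff override the random list. The documents do not support that. The allocation sentence does not exclude blocking or fixed totals, and step 4 shows routes to 6 + 6 that leave every tool assignment alone. Nor do the documents say that the clinician is booked before the tool is drawn. The very small probabilities in steps 2 and 3 depend on booking that ignores the tool.
- A reader might also infer that an uneven split biases the results. If the list is followed and booking is independent of it, chance imbalance adds variance, not bias. Step 5 puts that at 1% to 4% of the variance for moderate clinician differences and about 15% for very wide ones.
- The affected comparison is secondary. The stated hypotheses (at least 60%, at least 50%, at most 10%) concern each tool's own performance and do not need clinicians balanced between tools.

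The request to complete 6 and 6 may also be only a workload target. That is possible, but it is the only operator structure given and it sums exactly to the sample size. If the plan relies on one of the routes in step 4, that route needs a list type and a matching rule that are not written down.

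Balance by clinician is also not balance within diagnosis. With 6 children per clinician and tool, about 6 × 2/3 = 4 have ASD and 2 do not, varying by chance. Stratifying by clinician therefore helps sensitivity and specificity comparisons only in part.

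**Conclusion.** The concern holds as a gap in the allocation rule. As written, the plan does not secure 6 + 6 per clinician, and it does not secure 60/60 overall if simple randomisation is used (about a 7% chance of exact equality). With booking independent of the tool and 12 children each, a clinician reaches 6/6 with probability 0.23 to 0.24, and all ten with probability between 3.4 × 10^-7 and 4.7 × 10^-6.

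The consequence depends on what the site does. Following the list costs some precision in the between-tool comparison, modest unless clinicians differ widely. Choosing the clinician at discretion after the tool is known keeps tool assignment random but makes the pairing of rater and child non-random, which can bias that comparison. The size of such a bias cannot be derived from the documents. The per-tool accuracy estimates are largely unaffected either way. The change is worth making because it is cheap, it delivers the plan's own numbers, and the planned chi-square would not correct the imbalance.

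**What to change.** In the Randomization section, replace allocation by enrollment order for Aim 2 with a concealed list stratified by telemedicine clinician: 12 assignments for each of the 10 clinicians, 6 per tool, in randomly permuted order. Fix and record the clinician for the appointment before the assignment is released, and release it only after consent. If the clinician later has to change, log the change and keep the assigned tool. If every clinician completes 12 sessions, this gives 6 + 6 and 60/60 by construction.

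An acceptable alternative is a blocked 60/60 list with a preset, non-discretionary rule for matching clinicians to children. State both the list type and the rule.

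The cost is ten short lists in place of one, with no extra staff or visits. The small downside is predictability at the end of each list. In a permuted run of 6 + 6, the expected number of final assignments already determined is 12/7 = 1.7 per clinician, about 17 of 120. The family has consented by then, but someone who could see what remains might choose which clinician to book. Booking should therefore be set before anyone can see the remaining assignments.

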Can Novel Telemedicine Tools Reduce Disparities Related to Early Identification of Autism

NCT03847337

Protocol/SAP adapted from IRB Application approved on
02/04/2019

Can Novel Telemedicine Tools Reduce Disparities Related to Early Identification of Autism

Principal Investigator: [name]

Protocol/SAP adapted from IRB Application approved on 02/04/2019

Background

With an estimated prevalence of 1 in 68, early accurate identification and treatment of young children with Autism Spectrum Disorder (ASD) represent a pressing public health and clinical care challenge. There is growing evidence that (1) accurate, stable diagnosis of ASD is possible during the second year of life and (2) very young children with ASD receiving early behavioral intervention services demonstrate substantial gains in functioning. American Academy of Pediatrics (AAP) guidelines endorse universal screening for ASD at 18 and 24 months of age, and at any point when caregivers express concerns. Currently when children screen positive on ASD risk instruments in pediatric settings, providers are most commonly making referrals to (a) tertiary diagnostic centers with tremendous waits for evaluation (months to over a year) and/or (b) early intervention systems that, in absence of a diagnosis, typically provide very low levels of non-specific developmental service. Despite large-scale initiatives to promote screening and early diagnosis the average age of diagnosis in the US remains after four years of age for many children. Moreover, groups from traditionally underserved communities are much less likely to be diagnosed at young ages, including children from families of lower socioeconomic status, children whose parents report lower levels of educational attainment, children from racial and ethnic minority groups, and children in rural and geographically isolated communities. These diagnostic delays and health disparities contribute to substantial deleterious family stress and restrict access to meaningful evidence-based ASD intervention services.

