The clinician conducting the telemedicine procedure will be blind to the participant's existing diagnosis (autism or other developmental delay). Parents will be asked not to divulge this information in order to maintain research integrity.

Aim 2:

The clinician conducting the telemedicine procedure does not need to be blind because all participants will have necessarily not been evaluated before. The clinician who completes the gold standard diagnostic evaluation, however, will be blinded to the diagnostic impression and certainty of the clinician who conducted the telemedicine procedure. Parents will also be blinded to the results of the telemedicine procedure. They will not be blinded to any study procedures, the purpose of the study, or the results of the gold standard evaluation, which will include diagnostic feedback and recommendations.

This study does not involve deception.

6

Procedures:

Please indicate all procedures and activities performed for research purposes only and the frequency at which they occur in the study (e.g., skin biopsy, 3 times).

Procedure/Activity	Frequency
TELE-STAT (occurs in Aim 1 and Aim 2)	1 time, approximately 30 minutes
TELE-ASD-PEDS (occurs in Aim 1 and Aim 2)	1 time, approximately 30 minutes
Diagnostic Certainty Form	Approximately 5 minutes
Comprehensive interview with parents (occurs only in Aim 1)	1 time, 30 to 45 minutes
VABS-3 (occurs only in Aim 1)	1 time, 30 minutes
MSEL (occurs only in Aim 1)	1 time, 30 minutes
ADOS-2 (occurs only in Aim 1)	1 time, 30 to 45 minutes
Medical History/Background Information (occurs only in Aim 1)	1 time, 15 minutes
Parent Feedback Form (occurs in Aim 1 and 2)	1 time, 10 minutes
ALFA-Q (completed by clinicians and parents, both in Aim 1 and Aim 2)	

Data and Safety**Aim 1:**

Participants will be recruited from families who have come through our diagnostic clinics whose children have been diagnosed with autism or other developmental delays and who have previously signed consent to be contacted for research.

Aim 2:

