Specific Aim 1: We will deploy the *TELE-STAT* and *TELE-ASD-PEDS* to evaluate initial acceptability, feasibility, and potential clinical value for remote observation. Based on this feedback, we will modify instructions or procedures before the finalized tools are evaluated in the controlled trial of Aim 2. Given that this Aim relates to usability and entails an iterative design process, much of the data gathered will be compiled and analyzed descriptively. We therefore have carefully selected our sample size and embedded several explicit benchmarks of success to structure this critical design phase. To refine each instrument, we will recruit independent groups ($n = 30$ *TELE-STAT* and $n = 30$ *TELE-ASD-PEDS*) of children (18-36 months of age) and their caregivers, who have already been identified as having ASD (67%, $n = 20$) or non-ASD, but with other developmental concerns (e.g., language delay; 33%, $n = 10$). We will also recruit licensed psychologists from our clinical research center ($n=10$) that will coach parents through the procedures. All remote clinicians will have had previous training on the *STAT* and research reliability on the ADOS-2 as well as considerable expertise in routinely diagnosing ASD in children of this age range. This sample size ensures that the instruments will be utilized across a large number of clinicians and a large number of test cases representing both our primary population of interest (ASD) as well as our primary discriminator population (non-ASD developmental concerns).

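### Does the differing Aim 1 lower age limit (15 months in the inclusion criteria, 18 months in the statistical design) call for a change to the plan?

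*Combined protocol and SAP*

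**What the plan says.** Two parts of the combined protocol and SAP give an age range for Aim 1.

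- **Aim 1, Inclusion Criteria:** "\geq 15 months of age and \leq 36 months of age". The identical line stands in the Aim 2 list.
- **Statistical Design and Power, Specific Aim 1:** the two groups recruited to refine the instruments consist "of children (18-36 months of age) and their caregivers". A later sentence credits the remote clinicians with "considerable expertise in routinely diagnosing ASD in children of this age range", which points back to that range.

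For Aim 2, the Study Aims section refers to "new samples of clinically referred children (15-36 months of age", in agreement with the Aim 2 inclusion list.

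Two further statements determine who can enter Aim 1. The inclusion list requires "Previously evaluated and diagnosed with autism or other developmental delay", and the Data and Safety section says recruitment is from "families who have come through our diagnostic clinics whose children have been diagnosed with autism or other developmental delays". The accrual goal is "60 parents and 60 children in Aim 1; 120 parents and 120 children in Aim 2".

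**The concern.** Both ranges are in current text and both describe whom Aim 1 recruits. Take a child of 16 months who already has a diagnosis: the inclusion list admits that child, while the statistical section describes a group to which the child does not belong. Nothing calls 18-36 months a target or an expected subset of a wider eligible range.

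The possible stake comes from the order of the two aims. Aim 1 is where instructions and procedures are adjusted, and Aim 2 then tests the finished tools from 15 months. If 18-36 months governed, the youngest children admitted to Aim 2 would have had no part in shaping the tools, and the plan would not have disclosed this. One could then ask whether the tools had been tried across the whole age range in which they are judged.

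**Working it through.** **1. The plan's own figures.** Specific Aim 1 gives 30 children per tool, 20 with ASD and 10 without.

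- 30 + 30 = 60, which agrees with the accrual goal.
- 20/30 = 66.7% and 10/30 = 33.3%, which agree with the stated 67% and 33%.

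The plan gives no alpha, power or effect size for this sample. It justifies the size by the number of clinicians and test cases needed to find usability problems. None of these figures changes with the lower age limit.

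**2. Does any criterion use age?** Aim 1 has an ALFA-Q benchmark (mean rating above 4 of 5) and three accuracy criteria: at least 60% of children with ASD identified with certainty, at least 50% of those without, and at most 10% misclassified as ASD with certainty. Aim 2 repeats the three accuracy criteria as hypotheses. None is defined, stratified or adjusted by age.

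**3. How many children could be affected?** The documents give no age distribution, so any share is an assumption. With ages spread evenly over 15 to 36 months:

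- Share in the disputed band: (18 - 15)/(36 - 15) = 3/21 = 14.3%.
- Aim 1, per tool: 30 x 0.143 = 4.3 children.
- Aim 2, per tool: 60 x 0.143 = 8.6 children.

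For Aim 1 an even spread is probably too generous, because a child must have completed an evaluation and received a diagnosis before entry. The Background describes waits of months to over a year and late average diagnosis, although it also says that diagnosis in the second year of life is feasible. Small shares are therefore worth considering. The chance that a group of 30 contains no child of 15-17 months, even when such children are eligible, is:

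- at a 1% share, 0.99^30 = 0.74;
- at a 2% share, 0.98^30 = 0.55.

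At shares this low, the wider wording would more often than not give the same Aim 1 sample as the narrower one.

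**4. Could Aim 2 be disturbed?** The documents do not say that usability or accuracy differs at 15-17 months, so no effect can be estimated. An extreme scenario gives the scale. Each tool has 60 x 2/3 = 40 children with ASD in Aim 2. Suppose 14.3% of them are in the band, and identification with certainty falls from 60% to 0% there and stays at 60% elsewhere.

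- Shift in the overall percentage: 60 points x 0.143 = 8.6 points.
- 95% margin at 60% of 40: 1.96 x sqrt(0.6 x 0.4/40) = 0.152, about 15 points.

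Even total failure in the band moves the result by less than the sampling margin. Only the part of such a fall that piloting would have prevented could be charged to the age wording.

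**5. Is it a bias?** No. Aim 2 recruits new children from 15 months and compares the tools, as they then stand, with a blinded in-person assessment. If the tools worked less well in the youngest children, that would be part of the performance being measured. The estimate for the 15-36 month population remains valid whichever children informed the refinement.

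**The case for a change.** The strongest case for a change is that an eligibility contradiction is a defect whatever its size. The statistical section says who will be recruited, not who is expected; no rule of precedence is stated; and one of the two statements must be wrong. Aim 1 exists to find problems before the Aim 2 evaluation, so excluding the youngest eligible band would be a limitation that readers should know about. Aligning the text would take one phrase.

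Much of this stands. The two ranges differ, and if 18-36 months was intended, the absence of piloting at 15-17 months would be a fair limitation to report.

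What does not stand is that anything in the study turns on it. The narrower range lies inside the wider one, so every child described in the statistical section satisfies the inclusion list. A formal list headed as inclusion criteria is what staff apply at enrolment, and on that reading nothing is lost. On the other reading, Aim 1 remains a largely descriptive usability exercise, and the plan itself leaves the adequate test to Aim 2. The sentence on clinician expertise carries over the same slip and is not a second problem: experience at 18-36 months does not imply inexperience at 15-17. Correcting the phrase would permit these children without ensuring that any enrol.

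**Conclusion.** The inconsistency is confirmed, but it is clerical and no change to the plan follows. No sample size, benchmark, analysis or Aim 2 conclusion depends on whether the Aim 1 lower limit reads 15 or 18 months. The most natural reading is that the inclusion list governs, and the ages actually enrolled in Aim 1 will show whether children of 15-17 months took part.

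On size, an assumed even age spread puts about 4 of 30 Aim 1 children per tool in the disputed band, and the prior-diagnosis requirement could bring that close to zero under either wording. Within that same assumption, complete failure of a tool in the band would move the first Aim 2 benchmark by 8.6 points against a margin of about 15. That is a scenario and not an estimate, because the documents support no numerical effect.

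The conclusion rests on three things: that the inclusion list is applied at enrolment, or, if it is not, that Aim 1 stays descriptive; that Aim 2 enrols its own sample from 15 months, as both the Study Aims and the Aim 2 criteria state; and that children of 15-17 months do not make up a much larger share of enrolment than an even spread implies.
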